#### Rare, but Serious Risks

With the handling of medical and research records there is always the possibility of a breach of confidentiality. However, every effort is made to protect the privacy of participants. Every member of the Research Team is carefully trained and monitored about how to store, handle, and protect participant records.

Rare but more serious risks associated with the stellate ganglion block include bleeding from a broken blood vessel that results in a hematoma; injury to the nerves around the injection site; injury to the esophagus; pneumothorax; spinal cord trauma; infection of the tissues of the neck, nerves, bone or disc material in the area of the injection or IV placement; incomplete recovery of normal function.

Rare but more serious risks related to ropivacain used in the stellate ganglion block include feeling anxious, restless, confused, or like you might pass out; problems with speech or vision; ringing in the ears, metallic taste, numbness or tingling around the mouth, or tremors; seizure (convulsions); weak or shallow breathing; slow heart rate, weak pulse or fast heart rate, gasping, feeling unusually hot.

Rare but more serious risks if fluoroscopy is used for a prolonged time to guide the placement of the block are reddening of the skin, a very slight increase in the chance of contracting cancer, and a potential risk to an unborn embryo/fetus should a woman undergoing fluoroscopy be pregnant. Normally fluoroscopy will be used for less than one minute.

#### Concerns for Pregnant and Breastfeeding Women

It is not known whether ropivacaine can cause birth defects or other problems in an unborn child. Ropivacaine might be harmful to (1) an unborn child or (2) an infant who is breast-fed. Participants should not get pregnant or breastfeed while in this study.

#### Risks of PTSD Diagnosis regardless of Treatment

Possibility of increased suicidal risk. One of the risks of PTSD both in and out of treatment is attempted suicide, which can result in death.

#### Safeguards for Protecting Participants

For urgent issues, whether potentially related to the PE or to the stellate ganglion block, participants will be instructed to get help immediately by going to the Emergency Department open 24 hours at the Brooke Army Medical Center. For suicidal thoughts, participants can also be advised to call the suicide hotline, or go to a nearby civilian emergency room. Each week, the therapist will review the participant's progress and symptom levels and will provide individualized feedback to the participant as needed. Participants complete weekly self-report assessment measures that will assess PTSD severity, depressive symptoms, and suicidal ideation. This will allow therapists to closely monitor any increase in distress. Individualized safety planning will be utilized as needed by members of the treatment team. Any indication that the participant is considering suicide will be handled following the STRONG STAR Consortium SOPs in concert with the local site-specific policies and procedures. Participants can be seen at the Brooke Army Medical Center Emergency Department at any time.

The possible risks (i.e., temporary increase in distress and severity) associated with participation are reasonable in this context given the level of participant monitoring and access to research and clinical staff. We believe that the possible benefits from participating in this study outweigh the possible risks. However, if a service member decides against participation, he/she can still access mental health treatment through the Brooke Army Medical Center or Army One-Source.

#### **Research Monitor:**

[name], BPharm will serve as the DoD Independent Research Monitor. The duties of the research monitor shall be determined on the basis of specific risks or concerns about the research. The research monitor may perform oversight functions (e.g., observe recruitment, enrollment procedures, and the consent process for individuals, groups or units; oversee study interventions and interactions; review monitoring plans and UPIRTSO reports; and oversee data matching, data collection, and analysis) and report their observations and findings to the IRB or a designated official. The research monitor may discuss the research protocol with the investigators, interview human subjects, and consult with others outside of the study about the research. The research monitor shall have authority to stop a research protocol in progress, remove individual human subjects from a research protocol, and take whatever steps are necessary to protect the safety and well-being of human subjects until the IRB can assess the monitor's report. Research monitors shall have the responsibility to promptly report their observations and findings to the IRB or other designated official.

#### **8.2 Potential Benefits.**

Potential benefits of participation in this study may include a reduction in PTSD symptoms over the course of therapy. In addition, the knowledge gained from this study will serve to inform the most effective early interventions for the prevention and treatment of PTSD in active-duty military personnel.

### **9.0 ADVERSE EVENTS, UNANTICIPATED PROBLEMS, AND DEVIATIONS**

**9.1** Adverse Events will be assessed and monitored according to the established STRONG STAR SOP and the IRB of record's policies and procedures.

#### **9.2 Reporting Unanticipated Problems Involving Risks to Subjects or Others, Serious Adverse Events and Deaths to the IRB of Record.**

All adverse events, unanticipated problems involving risk to subjects or others, and deviations will be reported to the Institutional Review Board (IRB) in accordance with current IRB policy. UPIRSOs and recurrent non-compliance with study procedures will be reported promptly to the IRB. All adverse events that do not meet the UPIRSO criteria and deviations that are not non-compliance will be summarized at Continuing Review per the IRB of record's policy.

### **10.0 WITHDRAWAL FROM STUDY PARTICIPATION.**

528 Participation in the study may be discontinued by the principal investigator if continued participation is considered a  
529 danger to a participant's welfare. Reasons for discontinuation include: 1) a serious adverse event such that continued  
530 participation would be a danger to the participant; 2) clinical worsening for any reason that is deemed to necessitate non-  
531 study psychological or psychiatric treatment; 3) exacerbation of PTSD, anxiety, or depressive symptoms that the  
532 participant cannot tolerate; or 4) discontinuation would be in the participant's best interest. Participants deemed  
533 candidates for discontinuation will be discussed in the weekly conference calls with the therapist and the supervisor and  
534 will be brought to the attention of the PI for final decision.

535  
536 Participants who are discontinued from the study for any reason will be scheduled for a final evaluation within one week  
537 and given appropriate treatment referrals. If participants are discontinued due to a serious adverse event, they will  
538 continue to be followed clinically by the therapist and/or member of the research staff until the adverse event is resolved  
539 or becomes stable. If participants are discontinued for a medical or psychiatric reason, they will be given the opportunity to  
540 either complete the balance of their Massed-PE sessions or to receive a full course of Massed-PE after the condition has  
541 resolved or stabilized and the endpoint assessment has been completed. The reason the participants are discontinued  
542 from the study and any referrals made will be documented. Participants will be told they will be contacted for follow-up  
543 whether or not they complete the trial.

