## 7.4 Statistical Consideration

**7.4.1 Sample Size Estimation.** This study is a pilot investigation. Consequently, a power analysis was not conducted.

Estimate Required Sample Size	12
Screened Out/Excluded	12
Estimate Participant Drop Out / Withdrawal	3
Total Enrollment Requirement	27

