### 7.4.3 Data analysis.

Prior to statistical analyses, the data will be carefully inspected to identify such problems as unusual distributions, the desirability of transformations (e.g., logarithmic is often useful), missing data, and outliers. Data are also screened to identify potentially important covariates, i.e., variables (e.g., age) that are not of primary interest in the hypotheses but that

360 relate to the outcome measures (including such variables as covariates increases power and reduces bias).The primary  
361 software for statistical analyses is the SAS statistical system, that is widely available and well known. Our current version  
362 is SAS 9.4. We also have specialized software, including Stata 14, Mplus 8.2, and SPSS 25.

363  
364 The proposed study is in preparation for a larger clinical trial, with the primary goals of the pilot study being to  
365 demonstrate feasibility through evaluating recruitment, retention, and adverse events, and to estimate the magnitude of  
366 potential impact on selected outcomes. A total of 12 participants with PTSD to receive a combination treatment of Massed  
367 Prolonged Exposure with a stellate ganglion block will be included in the analysis. Assessments will be done at three time  
368 points (baseline, one- and three-months following the completion of treatment). Statistical analyses will be intent to treat,  
369 using all data from participants regardless of the extent of participation. We are requesting to consent up to 27  
370 participants to include 12 participants for analysis.

371  
372 The primary aim of this project is to evaluate the effectiveness and safety of a stellate ganglion block combined with  
373 Massed Prolonged Exposure for the treatment of PTSD in active duty and retired military service members. Tests of the  
374 descriptive hypotheses will involve calculation of the relevant proportions with 95% confidence limits based on PTSD  
375 diagnosis, PTSD symptom severity, and adverse events over the course of therapy, and dropout.

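### Under Section 7.4.3, month-1 and month-3 scores obtained after other PTSD treatment can count as successes of block plus Massed PE

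*Combined protocol and SAP*

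**What the plan says.** Hypotheses 1 and 2 (Section 3) concern patients who receive the block and Massed PE. They predict that more than half will be free of the CAPS-5 diagnosis, and that more than half will have a PCL-5 drop of at least 10 points, at one and three months. Section 7.4.3 estimates these proportions with 95% confidence limits by intent to treat, "using all data from participants regardless of the extent of participation". It names 12 participants for analysis.

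Section 10.0 governs discontinuation:

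- "Participants who are discontinued from the study for any reason will be scheduled for a final evaluation within one week" "and given appropriate treatment referrals".
- Those stopped for a medical or psychiatric reason may "either complete the balance of their Massed-PE sessions or to receive a full course of Massed-PE after the condition has" "resolved or stabilized and the endpoint assessment has been completed".
- All are told they will be contacted for follow-up "whether or not they complete the trial".
- A need for treatment outside the study is itself a listed reason for stopping: "clinical worsening for any reason that is deemed to necessitate non"-study psychological or psychiatric care.

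The enrolment table in Section 7.4.1 has a row "Estimate Participant Drop Out / Withdrawal" with the value 3. The term 'endpoint assessment' occurs only in Section 10.0 and is not defined. The procedures table in Section 7.3 has no column for the one-week final evaluation.

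**The concern.** Some participants who do badly are directed to other care, yet their later scores stay in the analysis. Nothing says how a score obtained after that care is classified. In a randomised trial, later treatment can at least be compared between arms. Here there is one arm and one proportion, so any help from later treatment is attributed to block plus Massed PE.

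At stake is the meaning of the two response rates that this pilot would carry into the larger trial. A reader will take them as what the combination achieves. They could partly reflect a second PE course or treatment given elsewhere.

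**Working it through.** **Which scores can be affected**

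Referral route. Section 10.0 gives referrals at discontinuation and ties them to no assessment. Follow-up continues and Section 7.4.3 keeps the score. A month-1 or month-3 value can therefore follow non-study treatment on any reading. The plan is equally silent on a completer who starts non-study PTSD treatment before month 3.

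Massed PE route. This depends on what 'endpoint assessment' means:

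- If it is the one-week final evaluation, further PE could start after that visit. A course takes 2 weeks, and Section 7.3 allows up to 3. The earliest finish is then 1 + 2 = 3 to 1 + 3 = 4 weeks after discontinuation, assuming the condition settles at once. That is well before month 3 and possibly before month 1.
- If it is the month-3 visit, this route is closed at both time points.

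**Plan's own figure**

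Section 7.4.1: 12 required + 12 screened out + 3 dropout or withdrawal = 27, as stated. No power calculation was done. The number starting treatment is not given; 12 + 3 = 15 is an inference, so both denominators are shown.

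**Effect of classification on the proportion**

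More than 50% means at least 7 of 12 or at least 8 of 15. One participant moves the proportion by 1/12 = 8.3 points or 1/15 = 6.7 points. The plan names no interval method; the limits below are exact (Clopper-Pearson), with lower limit Beta(0.025; x, n−x+1) and upper limit Beta(0.975; x+1, n−x).

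| Participants reclassified | Not a success (95% limits) | Success (95% limits) |
|---|---|---|
| 1 of 12 | 6/12 = 50.0% (21.1 to 78.9) | 7/12 = 58.3% (27.7 to 84.8) |
| 1 of 15 | 7/15 = 46.7% (21.3 to 73.4) | 8/15 = 53.3% (26.6 to 78.7) |
| 3 of 15 | 7/15 = 46.7% (21.3 to 73.4) | 10/15 = 66.7% (38.4 to 88.2) |

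**Chance of exceeding 50%**

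Assume the other participants succeed with true probability 0.5. Section 5 puts massed PE alone at about 50% falling below the diagnostic threshold. With m affected participants and c = 7 (n = 12) or c = 8 (n = 15), the chance is P(Bin(n−m, 0.5) ≥ c) if none of the m counts as a success, and P(Bin(n−m, 0.5) ≥ c−m) if all do.

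- n = 12, m = 1: 27.4% against 50.0%.
- n = 15, m = 1: 39.5% against 60.5%.
- n = 15, m = 3: 19.4% against 80.6%.

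If the affected participants also succeed half the time after later treatment, the chance is 38.7% for n = 12 and 50.0% for n = 15, whatever m is.

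**The case against.** The best defence is that a rule exists. Intent to treat with all observed data is a recognised treatment-policy approach, and choosing non-response instead is partly a matter of preference. That stands as far as it goes. But Section 7.4.3 does not mention later treatment, and the hypotheses credit success to the block and Massed PE.

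A reader might infer that a second PE course is bound to contaminate the results. The documents do not show this. Section 10.0 makes further PE wait for the endpoint assessment, and it uses a different name for the one-week visit, so a later visit may be meant. Only the referral route survives every reading.

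A reader might also infer that the response rate is certainly biased upward. Participants given other treatment may still be ill at follow-up and count as failures. Discontinuation can also be for a medical reason unrelated to response.

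Two further points have weight. The hypotheses are called descriptive, no decision hangs on crossing 50%, and the limits for 7/12 run from 27.7% to 84.8%. Affected participants could also largely be identified: Section 10.0 documents reasons and referrals, and the Health Questionnaire (Section 14.0) records mental health service use and psychiatric medication at baseline and both follow-ups. These lower the stakes, but they do not supply the missing rule.

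**Conclusion.** The concern holds in a limited form. As written, Sections 7.4.3 and 10.0 together allow a month-1 or month-3 score obtained after non-study PTSD treatment to count as a success of the combination. The same is true after a second PE course if the endpoint assessment is the one-week evaluation. Upward bias is possible, not established.

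One such participant is enough to change whether more than 50% is observed, with either 12 or 15 as denominator, when the count lies at the boundary. It would be tempting to cite the 20-point gap between 7/15 and 10/15 as the expected effect. It is an upper bound: it requires all three allowed dropouts to be treated further, assessed and successful. The allowance of 3 covers every kind of dropout, and someone who leaves without further treatment is not part of this problem. The number affected, their success rate and the denominator of 15 are assumptions.

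For a pilot meant to inform a larger trial, the rule should be fixed before the data are seen.

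**What to change.** Add to Section 7.4.3:

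- For Hypotheses 1 and 2, any participant, discontinued or completer, who receives a second full PE course or new non-study PTSD treatment before the assessment counts as not meeting the criterion at that assessment.
- A participant who only completes the balance of the original ten sessions is classified by the observed score.
- The observed-value (all-data) proportion is reported alongside, with the number of participants affected and the denominator used.

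In Section 10.0, reconcile 'endpoint assessment' with the final evaluation and with the month-1 and month-3 visits, so that it is clear which assessment is meant.

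The cost is a few sentences, with no change to care or visit timing. The information is already planned, but the protocol does not reproduce the Health Questionnaire items. The team should confirm that they separate new PTSD treatment from care already under way. The downside is a possibly less favourable response rate, and some participants whose benefit came from the study treatment may be counted as failures. Showing both proportions makes that visible.

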 665 indefinitely in the STRONG STAR Repository. Informed consent documents will be stored securely for a minimum of three  
 666 years following completion of the research; HIPAA authorizations will be stored for a minimum of six years IAW Federal  
 667 regulations. A protocol completion form will be filed with the IRB.

668  
 669 **14.0 DESCRIPTION OF ASSESSMENTS**

670 The majority of the measures listed below is commonly used, have adequate to good psychometrics, and are part of the  
 671 Consortium common data elements (CDE). As outlined in the National Research Action Plan, evidence-based CDEs and  
 672 measures for STRONG STAR studies will ensure comparability of results across the consortium as well as other clinical trials  
 673 and epidemiological studies of PTSD.

674  
 675 Demographics and Military Service Characteristics Form: The Demographics Form measures standard demographics  
 676 (race, gender, age) and military service information (e.g., rank). This measure will be administered at the baseline  
 677 assessment.

678  
 679 Life Events Checklist-5 (LEC-5). The LEC includes a list of 24 potentially traumatic life events commonly associated with  
 680 PTSD symptoms. The instrument was designed to facilitate the diagnosis of PTSD (Weathers, Blake, Schnurr, Kaloupek,  
 681 Marx, & Keane, 2013a). In this study, the LEC-5 will also be used to identify the index event and focus of the PTSD  
 682 treatment. For each potentially traumatic life event, respondents rate their experience of that event on a 5-point nominal  
 683 scale (1 = happened to me, 2 = witnessed it, 3 = learned about it, 4 = part of my job, 5 = not sure, and 6 = does not apply).  
 684 Each nominal point will be scored separately, as either 0 (=not endorsed by participant) or 1 (=endorsed by participant).  
 685 This measure will be administered at the baseline assessment, the one-month follow-up assessment, and the three-month  
 686 follow-up assessment.

687  
 688 Deployment Risk and Resilience Inventory-2 (DRRI-2) Combat Experience and Post-battle -Scales: High- and low-  
 689 intensity deployment stress exposure will be assessed using scales from the DRRI-2 (Vogt, Smith, King, & King, 2012).  
 690 The DRRI-2 is an update of the original DRRI (King, King, Vogt, Knight, & Samper, 2006), which was developed and  
 691 tested in three separate national samples of veterans of the first Gulf War. It has been revised and tested with  
 692 OEF/OIF/OND returnees (Vogt et al., 2008). The DRRI-2 provides an update of the DRRI’s assessment of deployment-  
 693 related factors to ensure the instrument’s applicability across a variety of deployment circumstances (e.g., different eras of  
 694 service) and military subgroups (e.g., men and women), as well as to validate updated measures in a contemporary

695 Veteran cohort (Vogt, et al., 2012). High intensity stressor exposures will be assessed using the DRRRI Combat  
696 Experiences and Aftermath of Battle subscales. Responses to these scales are on a 6-point Likert scale. The total score  
697 is the sum of the item scores, where higher scores signify greater exposure to combat or exposure to the consequences  
698 of combat, respectively. Both subscales have very good internal consistency ( $\alpha = .90$  to  $.92$ ) and construct validity (Vogt et  
699 al., 2012). This measure will be administered at the baseline assessment.

700 Mini-International Neuropsychiatric Interview (MINI-7.0) Psychosis and Mania modules. The MINI 7.0 is a short, structured  
701 clinical diagnostic interview designed to cover the major psychiatric disorders in DSM-5 and ICD-10. It is widely used in  
702 epidemiological studies and multi-site clinical trials. Responses to the interviewer's questions are rated as either "yes" or "no."  
703 As is the case on the SCID, there are skip-outs, which saves time. However, this means that the MINI cannot be used to  
704 index the severity of a given psychiatric problem, only caseness. When there are many skip-outs, the MINI takes ~15 minutes  
705 to administer. The MINI can be used to assess the full spectrum of psychiatric problems, or specific modules can be employed  
706 (e.g., the schizophrenia module to rule out thought disorder). This measure will be administered at the baseline assessment.

707 Health Questionnaire. The original Health Care Utilization (HCU) is a 16-item questionnaire developed in 2000 for [name]  
708 A. Resick's NIH grant, "Cognitive Processes in PTSD: Treatment II." The questionnaire was based on the 1999 Behavioral  
709 Risk Factor Surveillance System. The version that will be administered as part of the STRONG STAR Consortium has been  
710 modified to be of increased relevance to active-duty service personnel. The measure includes items regarding use of mental  
711 health services, current psychiatric medication, past psychiatric medication, hospitalization, and outpatient medical services,  
712 as well as items intended to assess changes in participants' military status. Tobacco/nicotine use will also be queried. This  
713 measure will be administered at the baseline assessment, the one-month follow-up assessment, and the three-month follow-  
714 up assessment.

715 Health Questionnaire – Supplemental for SGB. The Health Questionnaire – Supplemental for SGB is a 11-item self-report  
716 measure that assesses health conditions that would exclude individuals from receiving a stellate ganglion block. Respondents  
717 are asked to answer "yes" or "no" to each of the items. This measure was created specifically for this study and will be  
718 administered at the baseline assessment.

719 Self-Injurious Thoughts and Behaviors Interview (SITBI): The SITBI (Nock, Holmberg, Photos, & Michel, 2007) is a structured  
720 interview assessing the presence, frequency, and characteristics of self-injurious and suicidal thoughts and behaviors. The  
721 SITBI will be administered by an Independent Evaluator, who will instruct the participants to answer the questions based on  
722 their entire lifetime of experience. The SITBI has shown high interrater reliability, test-retest reliability, and concurrent validity  
723 (Nock et al., 2007). This measure will be administered at the baseline assessment, the one-month follow-up assessment, and  
724 the three-month follow-up assessment.

725 Depressive Symptoms Index-Suicidality Subscale (DSI-SS): The DSI-SS (Metalsky & Joiner, 1997) will be used to assess  
726 current suicidal ideation. The DSI-SS is a 4-item self-report measure of suicidal ideation that focuses on ideation, plans,  
727 perceived control over ideation, and impulses for suicide. It is being used as a core measure in the Military Suicide Research  
728 Consortium. Scores on each item range from 0 to 3, with higher scores reflecting greater severity of suicidal ideation.  
729 Instructions will instruct the participants to respond based on the past two weeks. A systematic review of measures of suicidal  
730 ideation and behaviors found that the DSI-SS had evidence of excellent internal consistency and concurrent validity  
731 (Batterham et al., 2014). This measure will be administered at the baseline assessment, the two interim assessments, the  
732 one-month follow-up assessment, and the three-month follow-up assessment.

733 The Clinician Administered PTSD Scale for DSM-5 (CAPS-5; Weathers, Blake, Schnurr, Kaloupek, Marx, & Keane, 2012):  
734 The CAPS-5 is structured interview that assesses the DSM-5 criteria for PTSD (Weathers et al., 2013). Each item is rated on  
735 a severity scale ranging from 0 (Absent) to 4 (Extreme/incapacitating) and combines information about frequency and intensity  
736 for each of the 20 symptoms. Additional items that are not included in the total score evaluate overall symptom duration,  
737 distress, impairment, dissociative symptoms, and global ratings by the interviewer. Validation studies are nearly complete to  
738 establish the psychometric properties of the CAPS-5 and findings will be reported in peer-reviewed publications. This  
739 interview is very similar to its predecessor, the CAPS for DSM-IV, which has been considered the gold standard for evaluating  
740 PTSD and demonstrated good reliability and validity (Weathers, Keane, & Davidson, 2001). In addition to reflecting diagnostic  
741 changes for PTSD in DSM-5, the CAPS-5 differs from the CAPS in that frequency and intensity ratings for each symptom are  
742 no longer scored separately, so the severity rating for each item determines whether a symptom is present or not. Subscale  
743 scores are calculated by summing severity scores for items in the following PTSD symptom clusters: re-experiencing,  
744 avoidance, negative alterations in cognitions and mood, and hyperarousal. Scores  $\geq 25$  indicate a probable diagnosis of  
745 PTSD. This measure will be administered at the baseline assessment, the one-month follow-up assessment, and the three-  
746 up assessment.

752 month follow-up assessment.

753  
754 PTSD Checklist-5 (PCL-5): The PCL-5 (Weathers, et al., 2010) is a 20-item self-report measure update of the PCL designed  
755 to assess PTSD symptoms as defined by the DSM-5. The PCL-5 is currently available and has been shown to have good  
756 psychometric properties. The PCL-5 evaluates how much participants have been bothered by PTSD symptoms in the past  
757 week (for all assessments during treatment) or the past two weeks (all other assessment time points) as a result of a specific  
758 life event. Each item of the PCL-5 is scored on a five point scale ranging from 0 (“not at all”) to 4 (“extremely”). This measure  
759 will be administered at the baseline assessment, the two interim assessments, the one-month follow-up assessment, and the  
760 three-month follow-up assessment.

761  
762 Patient Health Questionnaire-9 (PHQ-9): The PHQ-9 is a widely used and well-validated instrument for measuring the severity  
763 of depressive symptoms (Kroenke, Spitzer, & Williams, 2001). It consists of 9 items that assess both affective and somatic  
764 symptoms related to depression and depressive disorders; these 9 items correspond to the diagnostic criteria for DSM MDD.  
765 Respondents rate the frequency with which they have been bothered by depressive symptoms within the past two weeks on a  
766 scale ranging from 0 (“not at all”) to 3 (“nearly every day”). Scores on all items are summed to obtain a total severity score.  
767 Scores reflect no significant depressive symptoms (0-4), mild depressive symptoms (5-9), moderate depressive symptoms  
768 (10-14), moderately severe depressive symptoms (15-19), and severe depressive symptoms (>19). Respondents also  
769 indicate the degree to which their depressive symptoms have made it difficult for them to do their work, take care of things at  
770 home, or get along with other people, from “not difficult at all” to “extremely difficult.” The PHQ-9 has high internal consistency  
771 (e.g., alpha ranging from .83 to .92; Cameron, Crawford, Lawton, & Reid, 2008), and correlates strongly with other measures  
772 of depression (Kroenke et al., 2001). This measure will be administered at the baseline assessment, the two interim  
773 assessments, the one-month follow-up assessment, and the three-month follow-up assessment.

774  
775 Generalized Anxiety Disorder Screener (GAD-7): The GAD-7 (Spitzer, Kroenke, Williams, & Lowe, 2006) will be used to  
776 assess generalized anxiety symptomology. This is a 7-item measure that asks participants to rate the frequency with  
777 which they have been bothered by anxiety symptoms within the past two weeks on a scale ranging from 0 (“not at all”) to  
778 3 (“nearly every day”). Scores on all items are summed to obtain a total severity score. Scores reflect no significant  
779 anxiety symptoms (0-4), mild anxiety symptoms (5-9), moderate anxiety symptoms (10-14), and severe anxiety symptoms  
780 (>15). Respondents also indicate the degree to which their anxious symptoms have made it difficult for them to do their  
781 work, take care of things at home, or get along with other people, from “not difficult at all” to “extremely difficult.” The GAD-  
782 7 has been shown to have high internal consistency (e.g.,  $\alpha = .89$ ; Lowe et al., 2008) and has been shown to reliably  
783 discriminate between anxious and non-anxious diagnostic groups (Kroenke, Spitzer, Williams, & Lowe, 2010).

784  
785 Brief Inventory of Psychosocial Functioning: The Brief Inventory of Psychosocial Functioning (Marx et al. 2013) is a 7-item  
786 self-report instrument measuring respondents’ level of functioning in seven life domains: romantic relationship,  
787 relationship with children, family relationships, friendships and socializing, work, training and education, and activities of  
788 daily living. Respondents indicate the degree to which they had trouble in the last 30 days in each area on a 7-point scale  
789 ranging from “0 = Not at all” to “6 = Very much.” This measure will be administered at the baseline assessment, the one-  
790 month follow-up assessment, and the three-month follow-up assessment.

791  
792 Veterans Rand 12-Item Health Survey (VR-12): Because a certain level of PTSD symptoms is an occupational hazard  
793 among service members redeployed for combat, it is critical to pay close attention to functional capacities as an important  
794 index of intervention efficacy. The Veterans SF-36 (VR-36) was adapted from the RAND SF-36 Version 1.0  
795 questionnaire, and spans the range of health domains from physical to psychological health status. It includes two  
796 modifications. The first modification is an increase in the number of response choices for the role physical (RP) and role  
797 emotional (RE) items from a two point yes/no choice to a five-point likert scale (no, none of the time, yes, a little of the  
798 time, yes, some of the time, yes, most of the time, yes, all of the time). The second modification is the use of two items to  
799 assess health change, one focusing on physical health and one on emotional problems, in contrast to the one general  
800 change item in the RAND SF-36 (Kazis, Lee et al., 2004; Kazis, Miller, Clark et al 2004). The VR-36 has been widely  
801 used, distributed and documented in the Veterans Health Administration (VHA) with close to 2 million questionnaires  
802 administered nationally in six national surveys since 1996. The changes to the survey have increased the overall precision  
803 of the instrument and the discriminant validity of the physical and mental component summary scales (Kazis, Nethercot, et  
804 al 2006). The VR-36 is comprised of 37 items and eight scales: physical functioning, role limitations due to physical  
805 problems, bodily pain, general health perceptions, energy/ vitality, social functioning, role limitations due to emotional  
806 problems, and mental health. Also, there are two summary scales: a physical component summary (PCS) and mental  
807 component summary (MCS). Higher scores indicate better health. Each summary is expressed as a T score, which  
808 facilitates comparisons between the VA patients and the general U.S. population. The PCS and MCS scores provide at

809 least 90% of the reliable variance in the eight SF-36 concepts (Kazis & Wilson, 1998; Kazis, Wilson, et al., 1999). The  
810 Veterans SF-12 was developed from the Veterans SF-36 and adapted from the MOS SF-36. It includes fewer items for  
811 seven of the eight scales and provides 90% of the reliable variance in the two component summary measures using the  
812 Veterans SF-36. Using independent results from the Veterans Health Study and the 1996 National Survey of Ambulatory  
813 Care Patients, the results for the Veterans SF-12 corresponded very closely with the results for the Veterans SF-36  
814 (average differences of 0.06 points between them for PCS and 0.31 points for MCS; Kazis et al., 1996; Kazis & Wilson,  
815 1998). This measure will be administered at the baseline assessment, the one-month follow-up assessment, and the  
816 three-month follow-up assessment.

817  
818 Alcohol Use Disorders Identification Test (AUDIT): The AUDIT (Babor et al, 2001) will be used to identify people with  
819 hazardous or harmful patterns of alcohol consumption. The AUDIT is a 10-item screening measure, developed by the  
820 World Health Organization (WHO), with three subscales (alcohol consumption, drinking behavior, and alcohol-related  
821 problems) that are scored on a 4-point scale for a highest possible total score of 40. Among those identified as using  
822 alcohol in a harmful manner, 92% had scores of 8 or more, though determining a cutoff score should be left up to the  
823 clinician, depending upon the population being studied. The AUDIT has good internal consistency ( $\alpha = .80-.93$ ) as well as  
824 sensitivity and specificity (Saunders, Aasland, Babor, De La Fuente & Grant, 1993). This measure will be administered at  
825 the baseline assessment, the one-month follow-up assessment, and the three-month follow-up assessment.

826  
827 Insomnia Severity Index (ISI). The ISI (Morin, 1993) is a 7-item self-report measure that assesses perceived severity of  
828 insomnia. Each item uses a 4-point Likert type scale from 0 (not at all satisfied) to 4 (very much satisfied). The items sum to  
829 produce a total score (range 0 – 28). The ISI has an internal consistency alpha coefficient of 0.74, and has shown convergent  
830 validity with other measures such as the Pittsburgh Sleep Quality Index ( $r = 0.67$ ), the Dysfunctional Beliefs and Attitudes  
831 about Sleep ( $r = 0.55$ ), and sleep diaries ( $r$  ranges from 0.32-0.91) (Bastien, Vallieres & Morin, 2001). This measure will be  
832 administered at the baseline assessment, the one-month follow-up assessment, and the three-month follow-up assessment.

833  
834 Posttraumatic Cognitions Inventory (PTCI): The PTCI is a 36-item questionnaire that was developed to determine how an  
835 individual views the trauma and its sequelae in an attempt to understand both how PTSD develops and is maintained (Foa,  
836 Elhers, Clark, Tolin, & Orsillo, 1999). Using an emotional processing theory, Foa and her colleagues (1999) have suggested  
837 that PTSD is a consequence of disruptions in the normal processes of recovery when an individual has excessively rigid  
838 concepts about self and world rendering the person vulnerable if a traumatic event occurs. Thus the PTCI was developed as  
839 a measure of trauma-related thoughts and beliefs. It is comprised of three subscales (Negative Cognitions about the Self,  
840 Negative Cognitions about the World, and Self-Blame). The measure was tested in almost 600 adult volunteers recruited  
841 from two university PTSD treatment clinics as well as a university community. Approximately 65% ( $n=392$ ) of individuals  
842 reported having experienced a trauma in which their own life or that of another person was perceived to be in danger and their  
843 response at the time included intense terror, horror, or helplessness (Criterion A event). The remaining 35% ( $n=162$ ) denied  
844 such a traumatic experience. Of those who had experienced a trauma, 170 had PTSD symptoms of at least moderate  
